Pre-test measures, the intervention or control condition, and post-test measures will all be conducted on the same day during an approximately 1-hour study session. The pre-and post-test measures will take approximately 15 minutes to complete and the control and intervention condition will last approximately 30 minutes. No additional follow-up is planned.

Statistical Methods

In the analyses, we will examine the effect of the app on decisional capacity, controlling for sociodemographic characteristics and severity of delay. We will first conduct bivariate analyses comparing decisional capacity, decision making preferences, and likelihood of trial participation across the two study groups (tablet vs. standard procedure), using chi-square tests for categorical outcomes

and t-tests for continuous outcomes. In addition, we will conduct multiple regression models to compare study outcomes by study group after controlling for demographics and severity of developmental delay. Linear regression models will be conducted for continuous outcomes (e.g., decisional capacity scores, preferences) and logistic regression models for categorical outcomes (e.g., likelihood of participating in a hypothetical trial). Within these models, we will test for interactions between study group and demographic characteristics to identify differential impact of the intervention on particular subgroups. For example, testing an interaction between study group and severity of delay would allow us to determine if the tablet-based intervention is more or less successful among more impaired participants.

[figure not shown]
Power Analyses

To determine the recommended sample size, we have conducted a power analysis using a between-subjects design (i.e., participants are randomized to control or experimental group). See Figure 1 below. With a sample size of 70 (35 participants per group), we will have 90% power to detect an effect size of .75.

Figure 1. FXS Power Analysis

t tests – Means: Difference between two independent means (two groups)

Tail(s) = One, α err prob = 0.05, Allocation ratio $N2/N1 = 1$

Ethics and Confidentiality

This research protocol was reviewed and approved by two Independent Review Boards from the University of North Carolina Office of Human Research Ethics (IRB Number: 13-1128) and RTI International Office of Research Protection (0281200.276). This study has been registered with ClinicalTrials.gov (NCT02465931).

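### The 90% power claim assumes a one-tailed 5% t-test that the analysis plan neither justifies nor adopts; at 35 per group the power is 93% one-sided and 87% two-sided

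*Combined protocol and SAP*

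**What the plan says.** The Power Analyses section of the combined protocol and SAP describes a between-subjects comparison and concludes: "With a sample size of 70 (35 participants per group), we will have 90% power to detect an effect size of .75". The text under Figure 1 identifies the calculation as a t-test for two independent means with equal allocation, and gives the settings "Tail(s) = One, α err prob = 0.05". These settings are legible, so the point does not depend on the figure that is not shown.

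Statistical Methods plans bivariate group comparisons of decisional capacity, decision-making preferences and likelihood of trial participation, "using chi-square tests for categorical outcomes" and t-tests for continuous ones. Adjusted linear and logistic regressions follow. The section mentions neither one-sided nor two-sided testing, and gives no alpha. Its stated aim, to examine the app's effect on decisional capacity, is neutral as to direction. The only wording that touches on direction is in the interaction example, which asks whether the tablet is "more or less successful among more impaired participants".

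The Participants section sets an upper limit of 50 pairs, fewer than the 70 participants in the power statement.

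**The concern.** The only sidedness and significance level in the documents are in the settings of the power figure. The analysis plan does not repeat them and gives no reason for a one-tailed test. Two things follow.

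First, the decision rule is open. A two-sided p-value of 0.08, with the difference favouring the app, could be reported as non-significant. It could equally be reported as significant at one-sided p = 0.04 by pointing to the power section. According to the Blinding section, neither participants nor data collectors are blinded, which makes a rule fixed in advance more valuable.

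Second, the 90% may not describe the analysis that is run. If the tests are two-sided at 5%, power is below the stated figure. If they are one-sided at 5%, the chance of falsely declaring the app better is 5%, against 2.5% in that direction for a two-sided 5% test. A result in which the app does worse than the verbal review could then not be declared. The documents do not say which case applies.

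**Working it through.** **Inputs.** From Power Analyses: n = 35 per group, d = 0.75, alpha = 0.05, one tail, two-sample t-test, equal allocation. From Participants: a ceiling of 50 pairs. My assumption: 50 pairs means 50 people with FXS, split 25 and 25 under the 1:1 allocation in Trial Design.

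**Formula.** With n per group, df = 2n − 2 and the noncentrality parameter is d × √(n/2). Power is the probability that a noncentral t variable with these parameters exceeds the critical value t(1 − alpha) one-sided or t(1 − alpha/2) two-sided. For the two-sided test the lower tail is added; it is negligible here.

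**Step 1: the plan's own settings.** df = 68 and noncentrality = 0.75 × √17.5 = 3.137. The one-sided critical value at 0.05 is 1.668. Power = 92.8%. The stated 90% is not reproduced, but the plan errs on the cautious side. Normal approximation: Φ(3.137 − 1.645) = 93.2%.

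**Step 2: same sample, two-sided 0.05.** The critical value is 1.995. Power = 87.1%, which is 2.9 points below 90%. Normal approximation: Φ(3.137 − 1.960) = 88.1%, about 1.9 points below.

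**Step 3: what would give 90%.** The sample sizes are the smallest that reach 90% by the exact calculation.

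| | One-sided 0.05 | Two-sided 0.05 |
|---|---|---|
| Power at d = .75, 35 per group | 92.8% | 87.1% |
| d detectable with 90% power, 35 per group | .71 | .79 |
| Smallest n per group for 90% at d = .75 | 32 (64 in total) | 39 (78 in total) |

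A total of 70 matches neither column.

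**Step 4: at the enrolment ceiling, assuming 25 per group.** df = 48 and noncentrality = 0.75 × √12.5 = 2.652.

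| | One-sided 0.05 | Two-sided 0.05 |
|---|---|---|
| Power at d = .75, 25 per group | 83.4% | 73.8% |
| d detectable with 90% power, 25 per group | .84 | .94 |

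At this size the choice of tail costs 83.4 − 73.8 = 9.6 points, against 92.8 − 87.1 = 5.7 points at 35 per group.

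**The case against.** The strongest reply is that the plan discloses a one-tailed test, and that nothing in it commits the analysis to two-sided testing. A reader might infer from the chi-square tests and the interaction wording that the planned tests are non-directional, so that the stated power belongs to a different analysis. The documents do not go that far. Chi-square is reserved for categorical outcomes, whereas the power calculation is for a t-test, which is planned for continuous ones. The phrase "more or less successful among more impaired participants" illustrates an interaction with severity of delay and says nothing about the sidedness of the main comparison. Decisional capacity also has an obvious favourable direction, even though preferences and likelihood of participating have none stated. This part of the reply stands: two-sidedness is an inference, and the defect is silence.

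A reader might also take the failure to reproduce 90% under the one-tailed settings as a second shortfall. It is not, because 92.8% exceeds the claim. A value read off the power curve, a rounded effect size (.71 gives 90%) or a rounded-up sample size (64 suffices) could explain it, and the figure is not available to check.

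Finally, the two-sided gap at 35 per group is only 2 to 3 points, depending on the method. That is true, and it limits the seriousness of the point. None of this supplies the missing sidedness and alpha in the analysis plan.

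**Conclusion.** The point holds in a limited form. The power claim is calculated for a one-tailed 5% t-test. The analysis plan neither justifies nor adopts one-sided testing, and states no sidedness or alpha of its own. At 35 per group and d = .75 the 90% is exact on neither reading: it understates one-sided power (92.8%) and overstates two-sided power (87.1%).

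The documents do not show that the planned t-tests are two-sided, nor that the trial is underpowered under its own settings. The case rests mainly on the undefined decision rule, and only secondarily on a modest numerical error. I would grade it as a correction that should be made, below the level of an essential change.

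The enrolment ceiling matters more for achievable power than the tail does at 35 per group. If 50 pairs means 25 per group, two-sided power for .75 is about 74%. That figure depends on my reading of the cap. All the figures are for an unadjusted two-sample t-test with complete data and do not cover the regression models.

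**What to change.** 1. In Statistical Methods, state that all group comparisons are two-sided at a significance level of 0.05.
2. In Power Analyses, replace the power sentence with wording such as: With 35 participants per group, a two-sided 5% t-test has 87% power to detect an effect size of .75, and 90% power for .79. Correct the tail setting under Figure 1 to match.
3. Reconcile the 70 in Power Analyses with the ceiling of 50 pairs in Participants, and add the power at the ceiling. If it means 25 per group, that is 74% two-sided for .75, and 90% for .94. Without this, the new sentence would still overstate what the trial can achieve: 87.1 − 73.8 = 13.3 points.

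The cost is a few sentences and a less favourable stated power: about 3 points lower at 35 per group, and about 16 points (90 − 73.8) lower at the assumed 25 per group. No added enrolment and no change to study procedures is asked for.
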